6.4 Dermal Tolerability Assessments

Subject-assessed pruritus (itching), stinging/burning and dermatologist-assessed dryness and scaling will be summarized and displayed in terms of frequency count and proportion of subjects who reported at least a 1-grade worsening in severity from baseline at any time points over the study period.

For all dermal tolerability assessments, the scale (grade) was: 0 = none, 1 = mild, 2 = moderate, 3 = severe. A subject is classified as having had a at least 1-grade worsening from baseline for a timepoint if his change from baseline value ≥ 1 for the timepoint. The denominator used for calculating the proportion is the number of safety subjects who have baseline and at least one data of post-baseline dermal tolerability assessments.

There is no testing of any hypothesis or interval estimation of proportions with respect to dermal tolerability assessments.

Frequency count and proportion of subjects having had at least 1-grade worsening from baseline in dermal tolerability assessment parameters will be repeated and displayed by visit/timepoint. Summary statistics of dermal tolerability assessment parameters will also be presented by visit/timepoint.

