### 5 STUDY ENDPOINTS

### 5.1 Primary Endpoints

The primary endpoints of the study are:

- The incidence of treatment emergent adverse events (TEAEs) and serious adverse events (SAEs).
- The number and percent of subjects with at least a 1-grade worsening from baseline in the Dermal Tolerability Assessment at any timepoint over the treatment period.
- The number and percentage of subjects with at least a 1-grade worsening from baseline in the CTA at any timepoint over the treatment period.

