5.4 Subgroup Analyses for Efficacy Variables

Not applicable.

6. Safety Analyses

All safety analyses will be based on the safety population. Safety will be assessed primarily in terms of the frequency count and the binominal incidence proportion of the adverse events of interest. The binomial incidence proportion for a given event of interest during a certain period is defined as the number of unique patients who have experienced the event of interest in the period divided by the number of patients in the safety population, then multiplied by 100. Note that, for the calculation of the incidence proportion, the numerator is counted at subject level. Specifically, if a subject has experienced the event(s) of interest (at a given summarization level) more than once during the period, he/she is counted only once into the numerator. The binomial incidence proportion of an event is also called the percentage of subjects who have had such an event. The two terms are used interchangeably. The 95% CIs for binomial incidence proportion will also be calculated using the Clopper and Pearson exact method (via SAS[®] procedure Proc Freq).

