6.2 Adverse Events

Adverse events will be coded using MedDRA version 20.1 or later to give a PT and a SOC term for each event.

An adverse event (AE) is defined as any untoward medical occurrence in a clinical investigational patient administered a pharmaceutical (investigational) product and which does not necessarily have to have a causal relationship with this treatment.

All AEs will be included in by-subject AE listings. A separate listing will be created with all the distinct levels of SOC and PT, and the verbatim investigator description reported in the study. Sorting will be by earliest observed SOC, PT within SOC and then verbatim description.

A treatment-emergent adverse event (TEAE) is a post-baseline AE where (i) there is no pretreatment AE of the same MedDRA primary SOC and PT; or (ii) the maximum severity during the post-baseline period is greater than the maximal severity of any pre-treatment AE of the same MedDRA primary SOC and PT during the screening/baseline period. Note that the post-baseline period of the study starts upon the initiation of the energy-based therapy at Day 1.

Any AEs reported after signing of the Informed Consent Form and prior to the energy-based therapy on Day 1 are considered pretreatment AEs (PTAEs)

Relationship to study drug is categorized as 'related', 'possibly related', 'unlikely related', 'not related', and 'not assessable'. Relationship to trial medication as per investigator is not expected to be missing after data cleaning. However, if relationship is confirmed as missing, the AE will be considered as treatment related as per PI.

An overall summary of frequency count and the binomial incidence proportion with associated 95% CIs will be presented to describe the incidents of TEAEs. Note that 95% CIs of the binomial incidence proportion will be presented for the overall summary analyses of TEAEs, but not for the by-visit/timepoint analyses. Percentages and corresponding 95% CIs will be displayed to 1 decimal place.

Each type of AE will be tabulated by SOC and PT within SOC. The SOC and PT within SOC will be sorted by descending frequency. If a subject has multiple occurrences (start and stop) of an event associated with a specific SOC and PT, a patient will only be counted once in the incidence count for the SOC level and once at each PT within the SOC level.

The incidence of all TEAEs by SOC and PT will be presented for the following categories:

• Any TEAE

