6.5 Clinician's Telangiectasia Assessments (CTA)

Clinician's Telangiectasia Assessments (CTA) will be summarized and displayed in terms of frequency count and proportion of subjects who report at least a 1-grade worsening in severity from baseline at any time point over the study period.

For CTA, the scale was: 0 = clear skin, 1 = almost clear, 2 = mild, 3 = moderate, 4 = severe. A subject is classified as having had a at least 1-grade worsening from baseline for a timepoint if his change from baseline value ≥ 1 for the timepoint. The denominator used for calculating the proportion is the number of safety subjects who have baseline and at least one data of post-baseline CTA.

There is no testing of any hypothesis or interval estimation of the proportions with respect to CTA.

Frequency count and proportion of subjects having had at least a 1-grade worsening from baseline in CTA will also be presented by visit/timepoint. Summary statistics of CTA will also be presented by visit/timepoint.

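### The SAP rules out confidence intervals for two of the three primary endpoints (dermal tolerability and CTA worsening), so proportions from about 43 subjects would be reported with no statement of precision

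*SAP*

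**What the plan says.** Protocol 5.1 lists three primary endpoints in one unranked list. The first is the incidence of TEAEs and SAEs. The second is "The number and percent of subjects with at least a 1-grade worsening from baseline in the Dermal Tolerability Assessment at any timepoint" during treatment, and the third is "The number and percentage of subjects with at least a 1-grade worsening from baseline in the CTA at any timepoint" during treatment.

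The SAP treats them differently:

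- **Safety proportions in general (SAP Section 6, opening paragraph):** "The 95% CIs for binomial incidence proportion will also be calculated using the Clopper and Pearson exact method".
- **TEAEs (SAP 6.2):** "Note that 95% CIs of the binomial incidence proportion will be presented for the overall summary analyses of TEAEs". The by-visit tables carry no intervals. SAP 6.3 applies the same rule to SAEs.
- **Dermal tolerability (SAP 6.4):** "There is no testing of any hypothesis or interval estimation of proportions with respect to dermal tolerability assessments".
- **CTA (SAP 6.5):** "There is no testing of any hypothesis or interval estimation of the proportions with respect to CTA".

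For the last two, the SAP plans counts, proportions and summary statistics. The denominator is safety subjects with a baseline and at least one post-baseline value. Protocol 8.1.4 plans frequency distributions for both and does not supply an interval.

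**The concern.** The three primary endpoints are the same kind of quantity: subjects who had the event at any time, divided by subjects assessed. One gets an exact interval and two do not, and the SAP gives no reason. This is a stated rule, so the general sentence at the head of Section 6, which is written around adverse events of interest, cannot be read as covering the other two.

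A general preference for description does not explain the difference either. SAP 5.2 does no testing of efficacy variables, yet plans a distribution-free 95% interval for the median percentage change from baseline. The variable this applies to is facial redness by digital image analysis, an exploratory endpoint. An exploratory endpoint is thus given an interval that two primary endpoints are denied.

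Protocol 5.4 says the study is to find out whether the cream is safe and well tolerated as an adjunct. There is no control arm, so the interval is the main statistical guard against over-reading a low count. A report of no subject, or only a few, worsening would look reassuring while being compatible with materially higher true rates. The sample size does not fill the gap, because Protocol 8.2 sizes the study on treatment-related adverse events. Neither document states the precision expected for dermal tolerability or CTA.

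**Working it through.** **1. The plan's own sample size.** Inputs from Protocol 8.2: reference rate p0 = 0.082, margin δ = 0.14, Type I error 5%, power 80%, stated N = 43, enrolment about 45. The lower margin, 0.082 − 0.14, is negative and cannot bind, so only the upper margin matters: pU = 0.082 + 0.14 = 0.222. Using a normal approximation with 5% on that side, the null variance at pU and the alternative variance at p0:

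n = [z(0.95)·√(pU(1 − pU)) + z(0.80)·√(p0(1 − p0))]² / δ²

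= [1.645·√(0.222 × 0.778) + 0.842·√(0.082 × 0.918)]² / 0.14²

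= (0.6836 + 0.2309)² / 0.0196 = 42.7, rounded up to **43**.

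The stated figure reproduces on these settings. The calculation concerns treatment-related adverse events, so it fixes the number of subjects but says nothing about the other two primary endpoints.

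**2. Method for the missing intervals.** This is the Clopper-Pearson interval that SAP Section 6 already names. For x subjects with worsening out of n:

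- lower limit = the 2.5% quantile of Beta(x, n − x + 1), or 0 when x = 0
- upper limit = the 97.5% quantile of Beta(x + 1, n − x)

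When x = 0 the upper limit reduces to 1 − 0.025^(1/n). For n = 43 this is 1 − 0.025^(1/43) = 0.082. Its agreement with the 8.2% reference rate in Protocol 8.2 is a coincidence.

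**3. Results.** The counts are assumptions that span a plausible range, because the documents give no expected worsening rate for either endpoint.

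| Assumed count | n = 43: rate | n = 43: exact 95% CI | n = 45: rate | n = 45: exact 95% CI |
|---|---|---|---|---|
| 0 | 0% | 0 to 8.2% | 0% | 0 to 7.9% |
| 3 | 7.0% | 1.5 to 19.1% | 6.7% | 1.4 to 18.3% |
| 5 | 11.6% | 3.9 to 25.1% | 11.1% | 3.7 to 24.1% |
| 10 | 23.3% | 11.8 to 38.6% | 22.2% | 11.2 to 37.1% |
| 22 | 51.2% | 35.5 to 66.7% | 48.9% | 33.7 to 64.2% |

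At n = 43 the widths for 3, 5, 10 and 22 events are about 18, 21, 27 and 31 percentage points.

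**4. Sensitivity to the denominator.** The denominators in SAP 6.4 and 6.5 require a baseline and a post-baseline value, so they could fall below 43. With n = 40, 0/40 gives an upper limit of 8.8%, 3/40 (7.5%) gives 1.6 to 20.4%, and 10/40 (25.0%) gives 12.7 to 41.2%. Nothing material changes between 40 and 45.

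**The case against.** The strongest reply is that the SAP delivers the endpoints as the protocol defines them. Protocol 5.1 asks for a number and a percentage, Protocol 8.1 specifies n and percentage for categorical data, and Protocol 8.1.4 plans frequency distributions. The protocol promises no interval, so the two documents do not conflict on this point. The choice is open, pre-specified and in keeping with a descriptive Phase 4 study. No success threshold is set for either endpoint, no estimate is biased and no decision rule changes. Count and denominator will be shown, so a reader can compute the interval, and the SAP introduction allows additional analyses if the study report documents them.

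Most of that is accurate, and it limits the point to reporting. It does not remove it. A reader can equally derive the TEAE interval, yet the SAP reports that one. An interval is not a test, so including it would leave the study descriptive. Leaving it to an undocumented later choice is weaker than planning it.

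A second reply stands in full. Dermal tolerability is also scored one hour after energy-based therapy on Days 1 and 29 (Protocol Table 1), and on Day 1 that is before any study drug. SAP 6.4 counts worsening at any timepoint over the study period, so the percentage mixes device and drug effects. A confidence interval covers sampling error only and does not settle attribution.

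**Conclusion.** The concern holds. Two of the three primary endpoints have interval estimation expressly excluded, while the third has exact 95% intervals and nothing elsewhere in either document restores them.

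With 40 to 45 assessed subjects, an observed rate of zero still leaves an upper limit of about 8% to 9%. Rates near 7% carry an interval about 17 to 19 points wide, and rates near 23% one about 26 to 29 points wide. These figures rest on assumed event counts and on denominators close to the planned size.

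The point should be corrected, but it does not invalidate the analysis: the proportions themselves are correct as planned, and what is missing is the statement of how precisely they are known.

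**What to change.** In SAP 6.4 and 6.5, delete the exclusion of interval estimation and keep the statement that no hypothesis is tested. Add to each section that the proportion of subjects with worsening by one grade or more from baseline at any timepoint will be reported with a two-sided Clopper-Pearson 95% confidence interval, using the denominator already defined there. That gives five intervals: dryness, scaling, stinging/burning, pruritus and CTA. The by-visit and by-timepoint tables can stay without intervals, as they do for TEAEs in SAP 6.2.

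The report should also say that these intervals describe sampling error only and do not separate drug from device effects.

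The cost is an edit to two SAP sections and one added column in two tables. SAP Section 6 already names the method and the SAS procedure. Data collection, sample size and Type I error are untouched. The SAP introduction allows amendments before database lock.

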6.5 Clinician's Telangiectasia Assessments (CTA)

Clinician's Telangiectasia Assessments (CTA) will be summarized and displayed in terms of frequency count and proportion of subjects who report at least a 1-grade worsening in severity from baseline at any time point over the study period.

For CTA, the scale was: 0 = clear skin, 1 = almost clear, 2 = mild, 3 = moderate, 4 = severe. A subject is classified as having had a at least 1-grade worsening from baseline for a timepoint if his change from baseline value ≥ 1 for the timepoint. The denominator used for calculating the proportion is the number of safety subjects who have baseline and at least one data of post-baseline CTA.

There is no testing of any hypothesis or interval estimation of the proportions with respect to CTA.

Frequency count and proportion of subjects having had at least a 1-grade worsening from baseline in CTA will also be presented by visit/timepoint. Summary statistics of CTA will also be presented by visit/timepoint.

6.6 Vital Signs

Vital signs (e.g., systolic/diastolic blood pressure, heart rate, respiration rate, and body temperature) will be summarized by visit/timepoint using descriptive statistics.

6.7 Other Safety Analyses

All positive results of pregnancy tests will be listed.

6.8 Subgroup Analyses for Safety Variables

Not applicable.

7. Pharmacokinetic, Biomarker, Genomic, or Immunogenicity Data Analyses

Not applicable.

8. Health Outcomes Data Analyses

Analyses of certain patient reported outcome (PRO) measurements are described in Section 5.2. No other health outcomes data analyses will be conducted.

9. Interim Analyses

There is no interim analysis planned for this study.

10. Data Collected but not Analyzed

Not Applicable.

11. Deviations from Protocol

The modified Intent-to-Treat Population as defined in the Protocol (Oct 12, 2017) will not be used for reporting and analyses, since the intent-to-treat principle is commonly confined to randomized trials. Instead, an evaluable population, which is applicable for non-randomized trials, is defined in the SAP (See Section 2.1) and will be used for efficacy summaries.

Another deviation from the Protocol is that per protocol analysis population is defined and added into the SAP, and efficacy analyses will be repeated on the per protocol population if more than 20% of the evaluable subjects have had major protocol violations.

12. References

Journals or Software

SAS Institute Inc., Cary, NC (2013): SAS version 9.3

Allergan's Study Protocol

STUDY NUMBER

CMO-MA-MED-0530

STUDY TITLE

Multicenter, Open-Label, Interventional Study on the Safety and Tolerability of Oxymetazoline and Energy-Based Therapy in Subjects with Rosacea

13. Amendment(s)

Per protocol analysis population is defined and added to the SAP of Version 1.1. The per protocol population consists of all evaluable subjects who have not had any significant violations of the study protocol. Patients who have had significant violations of the study protocol will be identified before the analyses on the per protocol population being performed. Efficacy analyses will be repeated on the per protocol population if more than 20% of the evaluable subjects have had major protocol violations.

As those specified in the study protocol, major protocol violations (deviations) may include, but are not limited to:

(1) Inclusion/Exclusion criteria violations.

(2) Inadequate compliance with study drug.

(3) Prohibited medications and treatments taken. Refer to the Protocol sub-sections 5.6.10.1

and 5.6.10.2 for the list of prohibited medications and treatments.

(4) Significant deviations from the study drug administration schedule. Specifically, if a subject had ever deviated by more than 7 days from the scheduled visit windows, the subject will be considered as having had a major protocol violation.

The final list of the major protocol deviations will be defined during the data review meeting and before the final study database lock day.
